## Alterations to the SAP

See ‘Protocol Deviations’ on page 5.

## 2. Introduction

### Background and rational

Children and adolescents with cerebral palsy may be trapped in a vicious circle of low physical fitness, resulting in deconditioning that causes a further decrease in physical activity (PA), a lower quality of life and an increased risk of developing non-communicable diseases. Therefore, establishing a healthy and active lifestyle during childhood is even more important for individuals with a disability. However, the factors that influence habitual PA in children and adolescents with cerebral palsy remain unknown.

In Scandinavia, healthcare professionals offer standardized clinical examinations throughout childhood using the Cerebral Palsy Follow-Up Program (CPUP). Identifying objective predictors of PA from this national clinical quality database, as well as from proxy-reported questionnaires concerning quality of life, functional status, and personal factors by means of a conceptual statistical framework (e.g. the International Classification of Functioning, Disability and Health (ICF)) may be used for an elaborated knowledge on habitual PA in children with CP. Specifically, the results will allow for early detection and potential improved interventions.

### Objectives/hypothesis

The objective of this study is to identify and investigate potential predictors of habitual physical activity in children and adolescents with cerebral palsy. We hypothesize that potential predictors of habitual physical activity can be identified through the CPUP Program database, as well as in proxy-reported questionnaires, using the ICF as a conceptual statistical framework.

### 3. Methods

A protocol article for the study has been published (1).

#### Study design

The present study is a prospective clinical cohort study. Variables from historical registry data (from the Cerebral Palsy Follow-Up Program (CPUP)), along with proxy-reported questionnaires, will be used as predictive variables. Accelerometry data on physical activity will be used as outcome. For more details on the included variables, see the study protocol article (1).

#### Study size

The expected study size of 300-400 children, as mentioned in the protocol article, was obtained for consent given to participate. However, due to the COVID-19 pandemic, and consequences thereof, accelerometer data was only obtained for 123 children. Furthermore, due to the incompleteness of registered children in the CPUP database, only 78 of these children are eligible for analysis with CPUP data.

#### Timeline for the analysis

All analyses are to be performed after the SAP has been published on ClinicalTrials.gov (NCT04614207).

## 4. Statistical principals

### Confidence intervals and p-values

The significance level for statistically significant differences will be set at an  $\alpha = 0.05$  level (two-tailed testing) and will be presented as means and 95% confidence interval unless stated otherwise.

### Protocol deviations

Due to the COVID-19 pandemic and related shutdown of schools and after school activities, data collection was hindered and thus resulted in a reduced number of expected participants. Thus, deviations to protocol (as published (1), and initially registered at ClinicalTrials.gov November 3, 2020) are as follows:

- Data collection ended January 31st 2022
- It is not a requirement for the children to be registered in the CPUP
- Primary analysis: Due to a relatively large amount of included children not being registered in the CPUP, additional analyses will be performed on all children with accelerometry data (Model 1b):
  - o Model 1
    - a) Multiple linear regression analysis between accelerometer counts (response variable) and all CPUP variables within each ICF component (predictive variables), using the latest CPUP registration prior to accelerometer data collection.
    - b) Multiple linear regression analysis between accelerometer counts (response variable) and all questionnaire variables within each ICF component (predictive variables), using the questionnaire data.
- Secondary analysis. Due to the limited amount of children and adolescents included in the study, the protocol's model 2a (backward stepwise regression with accelerometer counts as the response variable and all included CPUP variables as predictive variables) will be performed for both model 1a and 1b using penalized regression. Furthermore, the initial model 2b (Multiple linear regression analysis between accelerometer counts (response variable) and all included variables as predictive variables) will be eliminated:
  - o Model 2
    - a) Penalized regression (lasso) with accelerometer counts as the response variable and covariates as chosen by lasso to obtain an optimal fit from model 1a as predictive variables to determine which variables to retain in the model.
    - b) Penalized regression (lasso) with accelerometer counts as the response variable and covariates as chosen by lasso to obtain an optimal fit from model 1b as predictive variables to determine which variables to retain in the model.
- The expected study size of 300-400 children was obtained for consent given to participate. However, due to the COVID-19 pandemic, and consequences thereof, accelerometry data was only obtained for 123 children. Furthermore, due to the incompleteness of registered children in the CPUP database, only 78 of these children are eligible for analysis with CPUP data.
- Due to the reduced number of expected participants, the model will not be testing the significance of CPUP data collection periods relative to the time in months from the measure of PA, for differences in prediction analyses between the following time periods:  $0 \leq 12$  months,  $13 \leq 24$  months and  $25+$  months

### Definition of the study population to be analyzed

Analysis will be performed on children and adolescents that have all completed the a-priori defined minimum number of valid wear days of the accelerometer (four, including one weekend day) (1).

## 5. Study population

### Screening data

Screening data to describe representativeness of the study population will be presented (age, gender, region of residence, CP type and subtype, GMFCS level) for children and adolescents participating in the study as well as for all additional children and adolescents registered in the CPUP database.

### Inclusion criteria

- Children and adolescents diagnosed with cerebral palsy,
- at a Gross Motor Function Classification System level I-III (independent gait function with or without assistive devices),
- born in the period 2003-2013,
- alive and living in Denmark.

### Recruitment

Social security number (CPR-number) and names of parents of a child diagnosed with cerebral palsy, retrieved from the Danish National Patient Register, was used to invite potential families to participate via secure digital mail (e-Boks) on November 3, 2020.

Information on recruitment will be included in the flow diagram (Figure 1).

### Withdrawal/exclusion

Potential participants (parents) received an invitation to participate via secure electronic mail (e-Boks). For those who did not respond to the invitation, a reminder to accept/decline consent to participate in the study was sent an additional two times. Participants who had given consent to participate, but had not stated an address to which the accelerometer could be sent, received a mail stating the importance of this information and requesting the address be stated. Families who returned an accelerometer and stated that they did not use it, were contacted via mail to ask whether they could be interested in receiving a new accelerometer.

Reasons for exclusion will be presented in the manuscript as well as Figure 1.

### Participant characteristics

Characteristics of participants will be outlined in Table 1.

[figure not shown]
## 6. Variable description

### Outcome

Daily average accelerometer counts will be used as outcome variable. The child/adolescent is encouraged to wear the belt with the Axivity AX3 accelerometer for seven consecutive days, but must have worn the accelerometer for a minimum of four days, including one weekend day, to be included in this study. The variable, daily average accelerometer counts, is weighted 5/7 and 2/7 for weekdays and weekend days, respectively.

Accelerometry data is collected 6-15 months post index date (see study diagram below).

### Study diagram

\*Latest CPUP registry entry, pre accelerometry collection, will be used as predictor variables for Model 1a + 2a.

\*\*Questionnaire data will be used as predictor variables for Model 1b + 2b.

### Exposure and adjustment variables

Questionnaire variables and CPUP variables within each ICF component will be used as predictors for predicting the outcome. See the protocol article for a list of included predictors (1).

Gender, region of residence, GMFCS level, and cerebral palsy subtype will be used as covariates and will be extracted from the CPUP database. Age will be calculated as age in years at index date. For non-participants, index date will be set at November 3, 2020.

For children and adolescents without CPUP data, gender, region of residence and GMFCS level will be extracted from parent-reported questionnaires. Age will be calculated as age in years at index date.

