## 7. Analysis

### Method of analysis

#### **Descriptive statistics – participant characteristics**

Gaussian distribution of numerical variables will be inspected by normal quantile plots (qq-plots). If variables are normally distributed, these will be presented as means with standard deviations (SD) and compared by two-sample t-tests. If variables are not normally distributed, they will be presented as medians and quartiles and compared by non-parametric equality-of-medians test.

Categorical variables will be presented as counts and proportions and compared with chi-squared test (or Fisher's exact test in case of counts below 5).

We will perform two descriptive comparisons: Participants with CPUP data versus participants without CPUP data, as well as, participants with CPUP data versus non-participants included in CPUP.

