## 8. Supplementary information

### SAP tables and figures

[figure not shown]

Figure 1. Flowchart of participants

Table 1. Participant characteristics

	Participants with CPUP data (n= )	Participants without CPUP data (n= )	Non-participants from CPUP (n= )
Age in years (mean (SD))			
At index date	xx (xx)	xx (xx)	xx (xx)*
Time in months from index date (mean (SD))			
To collection of questionnaire data	xx (xx)	xx (xx)	-
To collection of accelerometer data	xx (xx)	xx (xx)	-
To collection of CPUP data	xx (xx)	-	xx (xx)
Gender (n (%))			
Boy	xx (%)	xx (%)	xx (%)
Girl	xx (%)	xx (%)	xx (%)
Region of residence (n (%))			
Capital Region of Denmark	xx (%)	xx (%)	xx (%)
Central Denmark Region	xx (%)	xx (%)	xx (%)
Region of Northern Denmark	xx (%)	xx (%)	xx (%)
Region Zealand	xx (%)	xx (%)	xx (%)
Region of Southern Denmark	xx (%)	xx (%)	xx (%)
Cerebral palsy subtype (n (%))			
Spastic	xx (%)	-	xx (%)
Ataxic	xx (%)	-	xx (%)
Dyskinesia	xx (%)	-	xx (%)
Mixed/not classified	xx (%)	-	xx (%)
Missing data	xx (%)	-	xx (%)
GMFCS level (n (%))			
I	xx (%)	xx (%)**	xx (%)
II	xx (%)	xx (%)**	xx (%)
III	xx (%)	xx (%)**	xx (%)
Accelerometer count (mean (SD))	xx (xx)	xx (xx)	-

Abbreviations: GMFCS: Gross Motor Function Classification System, CPUP: Cerebral Palsy Follow-Up Program

Index date= date on which consent was given for participation, \*= the time of mass release of invitation to the study (November 3, 2020), \*\*=as reported by parents

Table 2. Prediction of physical activity using CPUP data predictive variables (Model 1a)

ICF constructs	Variables	Coef. [95% CI]	p-value	Adj.R 
Body Function & Structure				xx
	ROM	xx [xx,xx]	xx	
	Pain	xx [xx,xx]	xx	
	Muscle tone (modified Ashworth Scale)	xx [xx,xx]	xx	
	GMFCS level	xx [xx,xx]	xx	
Activities				xx
	FMS	xx [xx,xx]	xx	
	GMFM-66 score	xx [xx,xx]	xx	
	Ability to climb stairs	xx [xx,xx]	xx	
	Bikes	xx [xx,xx]	xx	
Participation				xx
	Participation in PT at school	xx [xx,xx]	xx	
	Participation in recreational activities	xx [xx,xx]	xx	
Personal Factors				xx
	Age	xx [xx,xx]	xx	
	Gender	xx [xx,xx]	xx	
	CP classification	xx [xx,xx]	xx	
Environmental Factors				xx
	Residence region	xx [xx,xx]	xx	
	Use of orthosis	xx [xx,xx]	xx	
	Use of wheelchair	xx [xx,xx]	xx	

Abbreviations: ROM: Range of motion; FMS: Functional Mobility Scale, PODCI: Pediatric Outcomes Data Collection Instrument; PT: physical training;

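### Table 1 uses different date rules for participants and for CPUP non-participants, so the age comparison carries a small one-way offset and the CPUP-timing row is not comparable (minor)

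*Combined protocol and SAP*

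**What the plan says.** **Age and index date.** Under Exposure and adjustment variables: "Age will be calculated as age in years at index date". The Table 1 footnote defines that date for participants: "Index date= date on which consent was given for participation". For the other group: "For non-participants, index date will be set at November 3, 2020". The Recruitment section and the same footnote identify this as the day the invitations were released. Under Withdrawal/exclusion, for families who had not responded, "a reminder to accept/decline consent to participate in the study was sent an additional two times".

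**CPUP record.** The note to the Study diagram reads: "Latest CPUP registry entry, pre accelerometry collection, will be used as predictor variables for Model 1a + 2a". The Outcome section adds: "Accelerometry data is collected 6-15 months post index date". The text does not say which registry entry describes a non-participant.

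**Comparison.** Under Descriptive statistics, one of the two planned comparisons is "participants with CPUP data versus non-participants included in CPUP". It uses t-tests or a test of medians for numerical variables, and chi-squared or Fisher's exact tests for categorical ones. Table 1 has a row for months from index to CPUP data, with entries for both of these groups. The Screening data section names the variables that are to describe representativeness: age, gender, region, CP type and subtype, and GMFCS level.

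**The concern.** The comparison is meant to show whether the analysed children resemble the other children in the registry. That matters here: 300-400 families consented, 123 children gave accelerometry and 78 can be analysed with CPUP data. A comparison of this kind is easiest to read when both columns are measured on the same clock, and here they are not.

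- Age is read at a later calendar date for participants than for non-participants, by the length of each child's consent delay.
- The participants' CPUP record is selected relative to accelerometry, an event that non-participants do not have. The rule cannot be carried over, and the text puts no other rule in its place.

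At stake is a modest distortion of one listed representativeness variable (age), and a timing row whose two columns cannot be set against each other although the general testing rule covers it. GMFCS level, subtype and region come from the same registry records, so their comparability depends on the same missing rule.

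**Working it through.** The SAP states no expected difference, power or sample size for this comparison, so there is no figure of its own to reproduce.

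**Inputs from the SAP.** Invitation 3 November 2020; data collection ended 31 January 2022; accelerometry 6-15 months after index; birth years 2003-2013; 78 participants with CPUP data; two-sided alpha 0.05.

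**Assumptions not in the SAP.** Birth years uniform; 300 to 1,000 non-participants; CPUP visits every 12 or 24 months in both groups, with the latest record uniformly spread over one visit interval before its cut-off.

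**Age: direction and ceiling**
1. Consent falls on or after 3 November 2020, so the shift (the mean consent delay) is zero or positive for participants.
2. From 3 November 2020 to 31 January 2022 is 454 days, or 454 / 30.4375 = 14.9 months.
3. At least 6 months must separate consent from accelerometry, so the latest feasible consent is about 31 July 2021. That is 270 days after invitation: 270 / 30.4375 = 8.9 months, or 270 / 365.25 = 0.74 years. The mean reaches this only if every participant consented on the last feasible day.

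**Age: size relative to spread.** The SD of a uniform 11-year range is 11 / √12 = 3.18 years. The last column is the chance that a two-sided 5% test rejects when the true age difference is zero.

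| Mean consent delay | Shift (years) | Shift / SD | Rejection rate, 78 vs 300-1,000 |
|---|---|---|---|
| 1 month | 0.08 | 0.03 | about 5.5% |
| 3 months | 0.25 | 0.08 | 9.5-10% |
| 6 months | 0.50 | 0.16 | 24-27% |
| 8.9 months (ceiling) | 0.74 | 0.23 | 45-51% |

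Example, 3 months and 500 non-participants: SE = 3.18 × √(1/78 + 1/500) = 3.18 × 0.1217 = 0.387; 0.25 / 0.387 = 0.65; Φ(0.65 − 1.96) + Φ(−0.65 − 1.96) ≈ 0.099.

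**CPUP timing.** Let A be the accelerometry lag after index, E the months from 3 November 2020 to the non-participants' record cut-off (not stated in the text), and T the visit interval.
- Participants' mean time from index to record: A − T/2.
- Non-participants' mean: E − T/2.
- Gap from the date rules: A − E. The visit interval cancels.

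| Non-participants' cut-off | Gap for A = 6 to 15 months |
|---|---|
| 3 November 2020 (E = 0) | +6 to +15 |
| 6 months later | 0 to +9 |
| 15 months later | −9 to 0 |
| 20 months later | −14 to −5 |

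With E = 0 and T = 12, the means are 0 to +9 months for participants against −6 for non-participants. Even the smallest gap would almost surely be declared significant: SD = 12 / √12 = 3.46, SE = 3.46 × 0.1217 = 0.42 with 78 vs 500, and 6 / 0.42 is about 14. With a mean lag of 10.5 months and a cut-off 10.5 months after invitation, the mean gap is zero.

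**After the fix.** With one reference date and one record cut-off in both groups, the date-rule component is zero for both age and record timing.

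**The case against.** There is a good case for leaving this alone.

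- **The differing index date is disclosed**, in the text and in the Table 1 footnote. This is true for age, but disclosure does not put the tested columns on one clock, and the footnote does not deal with the choice of CPUP record.
- **The age effect is small.** This stands. For a delay of 1-3 months it is 0.03-0.08 SD against 11 birth years, and no consent or reminder dates are given that would support a larger figure.
- **The timing row is not on the Screening data list**, and the Table 1 shell has no p-value column, unlike Tables 2 and 3. This also stands. The row describes data collection more than who took part, although the general testing rule does not exempt it.
- **The rule may be stated elsewhere.** The drawing of the study diagram and the cited protocol article are not in the text examined, and the surviving CPUP note concerns Models 1a and 2a. That Table 1 describes the same record is the natural reading, but it is not stated. If a rule for non-participants exists there, it should be repeated beside Table 1. The participants' own rule still cannot be applied to them.

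Three stronger readings are tempting, and the documents support none of them. A reader might infer that the Table 1 differences would come from the date rules alone, but responders and non-responders may truly differ in age or registration pattern. A reader might infer that the plan as written must produce a gap of around 10.5 months with a tiny p-value. That requires non-participants' records to be cut off at 3 November 2020, whereas the SAP fixes only their index date there; a later cut-off can shrink, cancel or reverse the gap. A reader might infer a direction of distortion for GMFCS level or region, but nothing in the documents gives one.

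**Conclusion.** The point holds in a limited form and is minor. The stated rules build a one-directional offset into the age comparison. It equals the mean consent delay: 0.08-0.25 years under an assumed mean delay of 1-3 months, and no more than about 0.74 years under the SAP's own dates. The CPUP-timing row cannot be compared between participants and non-participants, because the participants' rule depends on accelerometry and the text supplies none for the others. The resulting gap is 6-15 months only if non-participants' records stop at 3 November 2020. The more definite defect in that row is the missing record rule, not any particular number of months.

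The SD ratios and rejection rates rest on uniform birth years and an assumed 300 to 1,000 non-participants. The 0.74-year ceiling and the direction of the age shift rest only on dates in the SAP. Models 1 and 2 do not use non-participants and are unaffected.

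**What to change.** For the comparison of participants with CPUP data against CPUP non-participants only:

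1. Calculate age at 3 November 2020 in both groups.
2. Take GMFCS level, subtype, region and time to CPUP record from the latest registration on or before 3 November 2020 in both groups, and count that time from the same date.
3. Report participants' interval from the record used in Model 1a to the wear week on a separate line, without testing it against non-participants.
4. State these rules in the Table 1 footnote.

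Age at consent and the latest pre-accelerometry record can stay as they are for the models.

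The cost is a few lines of SAP wording and one extra pull from the same registry. Participants first registered in CPUP after 3 November 2020 drop out of this comparison, as do non-participants in the same position, so its participant column may hold fewer than 78 children. Their number should be reported.

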## 7. Analysis

### Method of analysis

#### **Descriptive statistics – participant characteristics**

Gaussian distribution of numerical variables will be inspected by normal quantile plots (qq-plots). If variables are normally distributed, these will be presented as means with standard deviations (SD) and compared by two-sample t-tests. If variables are not normally distributed, they will be presented as medians and quartiles and compared by non-parametric equality-of-medians test.

Categorical variables will be presented as counts and proportions and compared with chi-squared test (or Fisher's exact test in case of counts below 5).

We will perform two descriptive comparisons: Participants with CPUP data versus participants without CPUP data, as well as, participants with CPUP data versus non-participants included in CPUP.

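### Bounded or skewed variables are compared by the equality-of-medians test, which usually detects a difference less often than the rank-sum test at 78 versus 45 children

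*Combined protocol and SAP*

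**What the plan says.** Section 7 of the SAP, under descriptive statistics, sorts numerical variables by inspection of normal quantile plots. Of those judged normal it says "these will be presented as means with standard deviations (SD) and compared by two-sample t-tests". Of the rest it says "they will be presented as medians and quartiles and compared by non-parametric equality-of-medians test". It gives no reason for this test, and does not say whether a continuity correction or an exact p-value will be used.

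Two comparisons are planned: "Participants with CPUP data versus participants without CPUP data, as well as, participants with CPUP data versus non-participants included in CPUP". The Study size section gives the numbers for the first: "accelerometer data was only obtained for 123 children", and "only 78 of these children are eligible for analysis with CPUP data". The number of CPUP non-participants is not stated. Section 4 sets a two-tailed 0.05 level. The Screening data section gives representativeness as the reason for describing participants beside other children in CPUP.

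**The concern.** Once each value has been reduced to above or below the pooled median, its distance from the median no longer counts. The rank-sum test keeps the full ordering. For most bounded or skewed shapes, the discarded information is what shows a difference in location.

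Models 1a and 2a rest on the 78 children with CPUP data. Table 1 is where a reader will look to see whether those children resemble the 45 without. In such a table a non-significant p-value is easily taken as reassurance, and a test that misses real differences more often gives more of it.

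Several numerical rows of Table 1 are bounded or may be skewed. Age is limited by the criterion "born in the period 2003-2013", accelerometry falls 6 to 15 months after the index date, and accelerometer counts cannot be negative.

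**Working it through.** The SAP gives no power, effect size, SD or distribution for these comparisons, so there is no planned figure to reproduce. Shapes and shifts below are assumptions.

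**Inputs from the SAP.** 78 with CPUP data; 123 − 78 = 45 without (derived, not stated); two-sided α = 0.05.

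**Large-sample check.** For a shift of d standard deviations, power ≈ Φ(d·√(n₁n₂/(n₁+n₂))·√E − 1.96). E is the efficiency relative to the t-test: 12σ²(∫f²)² for the rank-sum test and 4σ²f(median)² for the median test. With d = 0.5, the first term is 0.5 × √(78 × 45/123) = 0.5 × 5.342 = 2.671.

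- Flat: E = 1 (rank-sum) and 1/3 (median). Power is Φ(0.711) = 76% versus Φ(−0.418) = 34%.
- Exponential: E = 3 and 1. Power is Φ(2.666) = 99.6% versus Φ(0.711) = 76%.
- Laplace: E = 1.5 and 2, so here the median test is ahead.

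These are approximations. The simulation below is the better guide to size.

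**Simulation at 78 versus 45, shift 0.5 SD** (0.5 scale units for Cauchy), with an uncorrected chi-squared median test:

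| Assumed shape | Median test | Rank-sum | Difference (points) |
|---|---|---|---|
| Flat | 35% | 70% | 35 |
| Lognormal (σ = 0.5) | 77% | 91% | 14 |
| Gamma, shape 2 | 68.5% | 89.0% | 20.5 |
| Exponential | 80–81% | 97% | 16–17 |
| t, 3 df | 91.3% | 94.6% | 3.3 |
| Laplace | 89.5% | 88.0% | −1.5 |
| Cauchy | 37.1% | 29.8% | −7.3 |

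A normal shape is left out because normal variables go to the t-test.

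**Dependence on the shift.** For a flat shape the loss is 17 points at 0.3 SD, 38 at 0.6 SD and 26 at 0.8 SD. For an exponential shift it falls from 30 points at 0.3 SD to 0.5 at 0.8 SD, where both tests are near 100%.

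**Age.** With whole-year ages flat over 11 years (assumed), a 2-year shift is detected 50.3% of the time by the median test and 88.5% by rank-sum; a 1-year shift, 16.3% and 35.1%. Both groups share the same birth years, however, so a pure shift overstates the case. If instead one group's ages tilt towards one end of the common range, the loss is about 12 to 16 points.

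**Error under no difference.** The uncorrected median test rejects about 6% of the time and rank-sum about 5%, so the lower power does not buy tighter error control. With a continuity correction the median test rejects about 2.5%, and its power losses grow, up to 52 points for a flat shape at 0.6 SD.

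**The case against.** The size of the loss is not a property of the design. A reader might infer from the table that 78 versus 45 costs a fixed number of points. The documents do not support that: they give neither shape nor effect size, and over the shapes and shifts tried the difference ran from about +38 to −11 points. This stands. Against it, the shapes that favour the median test are symmetric, unbounded and heavy-tailed, and nothing in the SAP suggests such a shape for age or time to accelerometry.

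The median test may seldom be used. The Table 1 shell prints mean (SD) for every numerical row, so the t-test is the default. Eligible birth years do not show that participants' ages are flat. Few rows are touched: four numerical rows have entries for both participant groups, and two for the comparison with non-participants. Gender, region and GMFCS level are compared by chi-squared or Fisher tests, so these rows are not the only evidence of resemblance. All of this stands, and it keeps the point small.

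A reader might also infer that the test makes the groups look more alike than they are. It does not. The medians and quartiles shown are the same whichever test is used; only the chance of a p-value below 0.05 changes. Nor does the SAP say that it will read non-significance as similarity; that is a risk of interpretation.

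Finally, the two tests address different hypotheses. With equal medians and different shapes, rank-sum rejected 22% of the time against 6% for the median test. Displaying medians and testing medians is coherent, so the change is not free. But where the purpose is to describe representativeness, sensitivity to any difference in distribution is wanted, and this downside is small.

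**Conclusion.** The point holds as a minor improvement. For bounded or skewed variables that reach the non-normal branch, the planned test is usually less powerful than rank-sum. At 78 versus 45 and an assumed 0.5 SD shift, the loss was about 14 to 35 points for the flat and skewed shapes examined. It was about 12 to 16 points for an assumed tilt within a shared bounded range, and small or reversed for heavy-tailed symmetric shapes. The consequence is that a real difference between children with and without CPUP data is more likely to be reported as non-significant.

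The figures assume that all 123 children remain in the analysis; both groups shrink if the minimum wear-day rule has yet to be applied. They do not extend to the comparison with non-participants. The test plays no part in Models 1 and 2, so the study's main conclusions are untouched.

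**What to change.** In section 7, under descriptive statistics, replace the test named for non-normal variables with the Wilcoxon rank-sum test, and keep medians and quartiles as the displayed summary. Add a sentence saying that a non-significant result in Table 1 is not evidence that the groups are similar. This second step is needed whichever test is used: rank-sum itself still misses a 0.5 SD shift about 30% of the time in the flat case (100% − 70%).

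The cost is one phrase, one sentence and one changed Stata command, with no new data. The note to the change should say that rank-sum tests a general difference in distribution and not the medians alone.
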